6.1.6. Statistical Methodology

The following general statistical models will be used in the analysis of efficacy, health outcomes, and selected safety measures for Periods 1, 2, 3, and/or the Follow-Up Period. In the detailed descriptions of each measure in the following sections of this plan, these models will be referred to and any exceptions or additions to the model will be stated as appropriate.

6.1.6.1. Logistic Regression Model

The primary analysis of categorical efficacy and health outcomes variables will use a logistic regression analysis with treatment, geographic region, and prior biologic CD therapy (prior biologic experience versus prior biologic naive) in the model. The proportions and 90% CIs will be reported. For each treatment comparison, an estimate of the odds ratio, corresponding Wald 90% CI, and p-value will be presented.

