10.3. Statistical Analyses

10.3.1. General Statistical Considerations

Statistical analysis of this study will be the responsibility of Lilly or its designee. A detailed SAP describing the statistical methodologies will be developed by the sponsor or its designee. SAS (Version 9.2 or higher, SAS Institute, Cary, NC, USA) will be used for the statistical analysis.

Any change to the data analysis methods described in the protocol will require an amendment ONLY if it changes a principal feature of the protocol. Any other change to the data analysis methods described in the protocol, and the justification for making the change, will be described in the clinical study report (CSR). Additional exploratory analyses of the data will be conducted as deemed appropriate.

Continuous data will be summarized in terms of the mean, standard deviation, minimum, maximum, median, and number of observations. Categorical data will be summarized as frequency counts and percentages. Unless otherwise specified, statistical tests of treatment effects will be conducted using 2-sided tests at an alpha level of 0.1. This will include the tests for continuous variables and categorical variables.

Treatment comparisons of categorical efficacy variables will be conducted using a logistic regression analysis with treatment, geographic region and prior biologic Crohn's disease therapy use (yes/no) in the model. The proportions and 90% confidence intervals (CI) will be reported.

Treatment comparisons of continuous efficacy and health outcome variables will be made using mixed effects for repeated measures (MMRM) analysis. When the MMRM model is used, the model includes treatment, geographic region, prior biologic Crohn's disease therapy use, baseline value, visit, and the interactions of treatment-by-visit and baseline-by-visit as fixed factors. The covariance structure to model the within-patient errors will be unstructured. If the unstructured covariance matrix results in a lack of convergence, the heterogeneous Toeplitz covariance structure, followed by the heterogeneous autoregressive covariance structure will be used. The Kenward-Roger method will be used to estimate the denominator degrees of freedom. Type III sums of squares for the least-squares (LS) means will be used for the statistical comparison; the 90% CI will also be reported.

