When necessary, additional analyses of categorical efficacy variables may be conducted to address sparse data or small sample sizes. Additional sensitivity analyses of continuous efficacy and health outcomes variables will be conducted using an analysis of covariance (ANCOVA).

Full details of these analyses including missing imputation methods and covariates will be provided in the SAP.

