10.3.3. Efficacy Analyses

10.3.3.1. Primary Efficacy Analyses

Rates of endoscopic response at Week 12, as defined in Section 10.1, will be analyzed. Subjects who do not achieve endoscopic response by Week 12 or who do not reach the Week 12 assessment will be considered to be non-responders at Week 12. Details of the NRI are provided in Section 10.3.1.2.

The primary endpoint analysis will utilize the statistical methodology described in Section 10.3.

Additional analyses of the primary endpoint may be considered and will be fully detailed in the SAP.

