6.1.6.2. Cochran-Mantel-Haenszel (CMH)

Secondary analysis of select categorical efficacy and health outcomes variables will be conducted using a Cochran-Mantel-Haenszel (CMH) test that stratifies by (that is, controls for) prior biologic CD therapy use. A Fisher's exact test may be utilized when deemed appropriate.

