6.1.6.3. Mixed Model for Repeated Measures (MMRM)

The primary analyses for all continuous efficacy and health outcomes variables will be based on the mixed model for repeated measures (MMRM) analysis method. The MMRM analyses will be conducted using a restricted maximum likelihood (REML)-based repeated measures approach. When MMRM is used, the model includes treatment, geographic region, prior biologic CD therapy use (prior biologic experience versus prior biologic naive), baseline score, visit, and the interaction of treatment-by-visit and baseline-by-visit as fixed factors.

The covariance structure to model the within-subject errors will be unstructured. If the unstructured covariance matrix results in a lack of convergence, the heterogeneous Toeplitz covariance structure, followed by the heterogeneous autoregressive covariance structure, will be used. The first structure to yield convergence will be used for inference. The Newton-Raphson with ridging optimization technique will be used to aid with convergence. The Kenward-Roger approximation will be used to estimate the denominator degrees of freedom. Type III sums of

squares for the least squares (LS) means will be used for the statistical comparison; the 90% CI will also be reported. Treatment group comparisons with placebo at Week 12 (Visit 8) will be tested.

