6.2. Adjustments for Covariates

The randomization at the beginning of Period 1 is stratified by previous biologic CD therapy: previous exposure to biologic therapy for treatment of CD, and naive to biologic therapy for treatment of CD. Unless otherwise specified, all efficacy and health outcomes analyses will include the stratification factor in the models. Geographic region will also be included as a covariate in the models.

Unless otherwise specified, analyses will be performed utilizing the methodology and covariates described in Section [6.1.6](#).

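### In the visible text, the binary-endpoint models omit the baseline score that the MMRM and ANCOVA include: the planned test is valid, but some power may be given up and chance baseline imbalance stays in the estimate

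*SAP*

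**What the plan says.** SAP 6.1.6.1 analyses categorical efficacy and health-outcome variables with a "logistic regression analysis with treatment, geographic region, and prior biologic CD therapy (prior biologic experience versus prior biologic naive) in the model". Protocol 10.3.1 has the same terms: "Treatment comparisons of categorical efficacy variables will be conducted using a logistic regression analysis with treatment, geographic region and prior biologic" use. The default covariate rule in SAP 6.2 is that "all efficacy and health outcomes analyses will include the stratification factor in the models. Geographic region will also be included as a covariate". SAP 6.1.6.2 adds, for selected variables, a "Cochran-Mantel-Haenszel (CMH) test that stratifies by (that is, controls for) prior biologic CD therapy use".

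For continuous variables, the MMRM in SAP 6.1.6.3 carries "baseline score, visit, and the interaction of treatment-by-visit and baseline-by-visit as fixed factors", and the ANCOVA in SAP 6.1.6.4 also has a baseline term.

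SAP 6.1.6 says that additions to a model will be stated with each measure. Tables AMAG.6.8 and AMAG.6.11 state none for a binary endpoint and list no continuous SES-CD comparison. Parts of the SAP are redacted, so this describes the visible text only.

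The documents leave room for more. Protocol 10.3.3.1 says "Additional analyses of the primary endpoint may be considered and will be fully detailed in the SAP", Protocol 10.3.1 says "additional analyses of categorical efficacy variables may be conducted to address sparse data or small sample sizes", and SAP 6.1.6.2 notes that a Fisher's "exact test may be utilized when deemed appropriate". No visible analysis uses that room for a baseline term. SAP 6.7 summarizes baseline characteristics by arm, which can show an imbalance but does not correct it.

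**The concern.** The same instrument is handled in two ways. Change in CDAI is adjusted for baseline CDAI; CDAI response and remission are not. Baseline SES-CD and the diary scores are collected in any case, so the omission saves nothing.

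Two things are at stake if baseline is prognostic. The comparison has less power than the same data could give. And in the one trial that is run, a chance difference in baseline between a dose arm and placebo moves the estimate up or down with nothing in the model to take it out. Two of the three comparisons with placebo use 30-patient arms, where such differences are larger, and the results are meant to guide further development.

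**Working it through.** **1. The plan's own figure.** Protocol 10.1 gives 60 per arm, 35% vs 15%, chi-squared test, two-sided 0.10.
- Null SE = sqrt(0.25 × 0.75 × 2/60) = 0.0791. Alternative SE = sqrt(0.15 × 0.85/60 + 0.35 × 0.65/60) = 0.0769.
- Power = Φ((0.20 − 1.645 × 0.0791)/0.0769) = Φ(0.91) = 81.8%. The stated 81% holds.

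**2. Validity.** In simulation (6,000 trials per setting) the planned Wald test at nominal 10% rejected a true null in 9.3–10.2% of trials at 60 vs 60 and 7.7–8.9% at 60 vs 30. It is not inflated.

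**3. Power with and without baseline.** The documents give no prognostic strength, so an odds ratio (OR) per SD of baseline is assumed. Setting: 60/60/30/30 subjects, three treatment indicators, region (40% assumed), prior biologic use (60% assumed, balanced within arm), rates held at 15% and 35%, Wald test at one-sided 0.05, 12,000 trials. Simulation error per cell is about sqrt(0.82 × 0.18/12,000) = 0.35 points.

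| Assumed OR per SD | 1000 mg (60 vs 60), current → adjusted | 30-patient arm vs placebo, current → adjusted |
|---|---|---|
| 1.0 | 82.6 → 82.3% | 68.5 → 68.4% |
| 1.5 | 82.6 → 83.4% | 69.4 → 70.2% |
| 1.8 | 82.3 → 84.3% | 69.0 → 71.0% |
| 2.7 | 82.3 → 87.2% | 69.2 → 74.2% |

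A separate two-arm simulation agrees: at OR 2.23, 81.3 → 84.5% (60 vs 60) and 68.0 → 71.6% (60 vs 30). If prior biologic use is itself prognostic (OR 1.8–2.0) and correlated 0.3–0.5 with baseline, the 1000 mg gain falls to about 0, 0.4–0.7, 1.2 and 3.2–3.9 points across the four rows.

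**4. Chance imbalance.** The SD of the difference in mean baseline, in baseline SD units, is sqrt(1/n1 + 1/n2).
- 30 vs 60: sqrt(1/30 + 1/60) = 0.224; P(|d| > 0.25) = 26.4%.
- 60 vs 60: sqrt(2/60) = 0.183; P(|d| > 0.25) = 17.1%.

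Half of each falls in either direction. Correlated prior biologic use, as in step 3, lowers the 26% to 20–24%. In the two-arm simulation at 60 vs 60, the correlation between imbalance and the estimated log odds ratio rose from about 0 (OR 1.0) to 0.33 (OR 2.7) under the planned model, and was about 0 with baseline included.

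With no true effect (15% in every arm) and imbalance above 0.25 SD in a 30-patient arm, the current model's median odds ratio at OR 1.0, 1.5, 1.8 and 2.7 was 0.99, 1.15, 1.23 and 1.39 when imbalance favoured LY3074828, and 1.00, 0.84, 0.80 and 0.71 when it did not. With baseline included it was 0.97–1.00.

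**5. What changes on the reported scale.** At 60 vs 60 and OR 2.23, the median log odds ratio goes from 1.15 to 1.30 and its SE from 0.464 to 0.503. The interval widens on the log-odds scale, while the conditional effect being estimated lies further from zero. On the standardised risk-difference scale, variance changes by +1% (OR 1.0) to −12% (OR 2.7).

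**6. Endpoints with absolute cut-offs.** Entry thresholds are in Protocol 6.1; remission definitions are in Protocol 9.1.2.
- Endoscopic remission, ileal-colonic: from 7 to 3 needs 1 − 3/7 = 57%; from 20 to 3 needs 1 − 3/20 = 85%. Isolated ileal: from 4 to 1 needs 1 − 1/4 = 75%. The subscore rule applies as well.
- PRO remission: from SF 4 and AP 1, SF must fall 1 − 2.5/4 = 37.5% and AP not at all; from SF 8 and AP 2.5, the falls are 1 − 2.5/8 = 69% and 1 − 1/2.5 = 60%.

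**7. Room in the models.** Expected responders for the primary endpoint: 60 × 0.15 + 120 × 0.35 = 51. Terms: 3 treatment + region + prior biologic = 5, or 6 with baseline; 51/6 = 8.5 events per term. Endoscopic remission at an assumed 5% vs 18% gives 60 × 0.05 + 120 × 0.18 ≈ 25 events, about 4 per term with 6 terms.

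**The case against.** The strongest reply is that this is a preference. Protocol and SAP agree with each other, the binary models adjust for the stratification factor and region as pre-specified, and a baseline term is routine in a model for change but not obligatory in a logistic one. That stands: there is no inconsistency between the documents and no error.

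A reader might infer that the planned test inflates false positives. In trials selected for imbalance above 0.25 SD favouring LY3074828 in a 30-patient arm, one-sided error under the current model is 8.6–12.5% at assumed OR 1.5–2.7. But it is 1.2–3.0% when the imbalance goes the other way, and over all trials it is 5.2–5.4% against 5.1–5.5% with baseline. Even at OR 1.0, where both directions should match, the simulated values were 5.7% and 4.8%, which shows the noise. Nothing supports a claim of inflation.

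A reader might also infer that the reported odds ratio would gain a narrower interval. Step 5 shows the opposite. The gain is in power and in removing chance imbalance.

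Endoscopic response is already measured against baseline, so a further link with baseline SES-CD is hypothetical. For the remission endpoints the cut-offs make a link more plausible, but its size would need assumed rates, baseline distributions and a mechanism; none is in the documents, so no gain is claimed there. Sparse events also count against changing the primary model for those endpoints. At an assumed 6% in every arm, the chance that some arm has no events is 1 − (1 − 0.94^30)² × (1 − 0.94^60)² = 32%, so a rule that switches models on observed events would often be triggered.

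Protocol 10.3.5 does plan models of change in SES-CD and of subject factors, but as exposure-response work. It does not adjust the randomized comparison.

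**Conclusion.** The point holds as an optional improvement. In the visible text, the logistic and CMH analyses leave out a baseline score that the MMRM and ANCOVA include. The planned test is valid and the 81% power is correct.

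For the primary endpoint, the possible loss is about 0 to 5 points of power over assumed odds ratios of 1.0 to 2.7 per SD. It is about 1 to 3 points for a moderate link, and less if prior biologic use already carries part of the information. An imbalance above 0.25 SD has a 26% chance in each 30-patient arm and 17% in the 60-patient arm. Those probabilities follow from arm size alone; whether an imbalance shifts the estimate depends on prognostic strength that the documents do not give. If baseline is not prognostic, nothing is gained and at most a fraction of a point of power is lost.

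**What to change.** Make the change before unblinding, because a covariate chosen after an imbalance has been seen is open to challenge.

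- **Primary endpoint.** In SAP 6.1.6.1 and 6.2 and Protocol 10.3.1, add continuous baseline SES-CD to the logistic model for Week 12 endoscopic response. Keep the current model and CMH as pre-specified sensitivity analyses.
- **Other endpoints.** For endoscopic remission and the single-measure PRO, CDAI and questionnaire responder endpoints, add the matching baseline score in a pre-specified supportive analysis. Leave the planned model as primary where events are sparse. Leave composites unchanged.
- **Missing baseline.** Impute a missing baseline covariate with the mean pooled over all arms, so that no randomized subject is dropped. Few should be missing, since SES-CD and SF/AP are entry criteria.
- **Reporting.** State that the adjusted odds ratio is conditional on baseline, and that its interval on the log-odds scale may be wider even though the test has equal or greater power. A standardised risk difference may be reported with it.

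The cost is wording and one extra term in the primary model. No new data are needed. The real price is that the odds ratio changes meaning, which the reporting statement covers.

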6.1.6.2. Cochran-Mantel-Haenszel (CMH)

Secondary analysis of select categorical efficacy and health outcomes variables will be conducted using a Cochran-Mantel-Haenszel (CMH) test that stratifies by (that is, controls for) prior biologic CD therapy use. A Fisher's exact test may be utilized when deemed appropriate.

6.1.6.3. Mixed Model for Repeated Measures (MMRM)

The primary analyses for all continuous efficacy and health outcomes variables will be based on the mixed model for repeated measures (MMRM) analysis method. The MMRM analyses will be conducted using a restricted maximum likelihood (REML)-based repeated measures approach. When MMRM is used, the model includes treatment, geographic region, prior biologic CD therapy use (prior biologic experience versus prior biologic naive), baseline score, visit, and the interaction of treatment-by-visit and baseline-by-visit as fixed factors.

The covariance structure to model the within-subject errors will be unstructured. If the unstructured covariance matrix results in a lack of convergence, the heterogeneous Toeplitz covariance structure, followed by the heterogeneous autoregressive covariance structure, will be used. The first structure to yield convergence will be used for inference. The Newton-Raphson with ridging optimization technique will be used to aid with convergence. The Kenward-Roger approximation will be used to estimate the denominator degrees of freedom. Type III sums of

squares for the least squares (LS) means will be used for the statistical comparison; the 90% CI will also be reported. Treatment group comparisons with placebo at Week 12 (Visit 8) will be tested.

6.1.6.4. Analysis of Covariance (ANCOVA)

A sensitivity analysis of treatment comparisons of continuous efficacy variables may be conducted using analysis of covariance (ANCOVA) with treatment, geographic region, baseline value, and prior biologic CD therapy use (prior biologic experience versus prior biologic naive) in the model. Type III sums of squares for the LS means will be used for the statistical comparison; the 90% CI will also be reported.

6.2. Adjustments for Covariates

The randomization at the beginning of Period 1 is stratified by previous biologic CD therapy: previous exposure to biologic therapy for treatment of CD, and naive to biologic therapy for treatment of CD. Unless otherwise specified, all efficacy and health outcomes analyses will include the stratification factor in the models. Geographic region will also be included as a covariate in the models.

Unless otherwise specified, analyses will be performed utilizing the methodology and covariates described in Section [6.1.6](#).

6.3. Handling of Dropouts or Missing Data

6.3.1. Non-Responder Imputation (NRI)

The primary outcome is the proportion of subjects with endoscopic response at 12 weeks. For this and other categorical efficacy endpoints, non-responder imputation (NRI) will be used for missing clinical assessment values. Specifically, all subjects who discontinue from the study treatment at any time prior to Week 12 for any reason or fail to have an adequate Week 12 efficacy assessment, will be considered a non-responder at Week 12. Randomized subjects without at least 1 postbaseline observation will also be defined as non-responders for the NRI analysis.

Similarly, subjects who discontinue from the study treatment for any reason at any time prior to Week 52 for any reason or fail to have an adequate Week 52 efficacy assessment, will be considered a non-responder at Week 52. Subjects (including non-improvers and placebo subjects) without at least 1 Period 2 observation will also be defined as non-responders for the NRI analysis at Week 52.

The NRI may be applied at any time point specified for analysis. In general, a subject will be defined as a non-responder from the time of treatment discontinuation and onward. If a measurement is taken at the time point of treatment discontinuation, this measurement will be used to define if a subject is a responder or not for the particular time point; measurements taken at subsequent time points will be defined as non-responder.

6.3.2. Modified Baseline Observation Carried Forward (mBOCF)

A modified baseline observation carried forward (mBOCF) analysis will be performed on key continuous efficacy endpoints.

This is both a sensitivity analysis and an analysis for regulatory agencies that prefer an alternative to MMRM. For subjects discontinuing investigational product due to an adverse event (AE), the baseline observation will be carried forward to the corresponding primary endpoint for evaluation. For subjects discontinuing investigational product for any other reason, the last non-missing postbaseline observation before discontinuation will be carried forward to the corresponding endpoint for evaluation. Randomized subjects without at least 1 postbaseline observation will not be included for evaluation with the exception of subjects discontinuing study treatment due to an AE.

6.4. Multicenter Studies

This study will be conducted by multiple investigators at multiple sites internationally. Randomization to treatment groups will not be stratified by country. However, the countries will be categorized into geographic regions for use as a covariate during applicable analyses.

Unless otherwise specified, the statistical analysis models will adjust for geographic region (United States [US] versus non-US).

6.5. Multiple Comparisons/Multiplicity

No multiplicity adjustment will be done for testing primary or secondary hypotheses for this Phase 2 study.

6.6. Subject Disposition

All subjects who discontinue from the study will be identified, and the extent of their participation in the study will be reported. If known, a reason for their discontinuation will be given.

Disposition data will be summarized by treatment group for Periods 1, 2, 3, and Follow-Up using the ITT Population. Period 1 will use the treatment groups defined for the ITT population. Periods 2, 3, and Follow-Up will use the treatment groups for EHO Group 2.

The number and percentage of subjects randomized and completing the study or discontinuing the study drug/study early will be presented. Reasons for discontinuing the study drug and reasons for discontinuing study will be summarized.

6.7. Subject Characteristics

Demographic and baseline disease characteristics, including medical history and detailed CD history, will be summarized by treatment group and overall for the ITT population.

Demographic characteristics will include sex, weight, height, smoking habits, race and ethnicity. Age and body mass index (BMI) will be calculated and summarized. Baseline disease

characteristics, such as age at diagnosis, location and duration of disease, prior biologic CD therapy, will be summarized.

No inferential analysis for the comparability of demographic and baseline disease characteristics across treatment groups will be performed.

6.8. Treatment Compliance

Subjects who are noncompliant according to the definition in Section 7.6 of the protocol will be listed by treatment and will also be counted as protocol deviations. A subject will be considered noncompliant if he or she fails to attend for administration of study medication within the required treatment window as defined in the Schedule of Activities (Section 2) in the protocol, or if the prescribed dosage was not administered.

Study treatment administration data at all treatment visits will be listed for the ITT population.

